5. STUDY POPULATION

Four thousand (4000) adults ≥ 50 years of age with self-reported symptoms of COVID-19 for no more than five days prior to screening, and who test positive for SARS-CoV-2 antigen at screening or have a

positive SARS-CoV-2 RT-PCR within 2 days prior to screening, and who are at risk of progression to severe disease, will be enrolled.

Interested volunteers will be invited to participate in the informed consent process as described in Section 12.2. Written informed consent will be obtained prior to any screening procedures.

Volunteers may be re-screened if they are found not to have COVID-19 at the time of the initial screening, but develop a further, and distinct, acute illness suggestive of COVID-19 at a later stage.

The following eligibility criteria will be used to select study participants.

5.1 Inclusion criteria:

1. Able and willing to provide written or electronic informed consent prior to any study-specific procedure.
2. Age ≥ 50 at the time of signing the informed consent form.
3. Women of reproductive potential must have a negative pregnancy test at screening and be using a highly effective method of contraception. Highly effective methods of contraception include:
 - a. Hormonal methods of contraception for at least 14 days prior to screening (including oral contraceptive pills, injectables, or implants)
 - b. Intrauterine devices from at least 7 days prior to screening (including hormone-releasing, and non-hormone-releasing devices)
 - c. Bilateral tubal ligation
 - d. Engaging exclusively single-sex relationships
 - e. Sexual abstinence
4. A male participant must wear a condom when engaging in any activity that allows for passage of ejaculate to another while taking the investigational product. Male participants should also be advised of the benefit for a female partner to use a highly effective method of contraception as condom may break or leak.
5. Self-reported symptoms of COVID-19 with onset no more than five days prior to screening informed consent including at least one of, fever or chills, cough, sore throat, rhinorrhoea or rhinitis or sinusitis, shortness of breath, headache, myalgia, new onset anosmia or ageusia, nausea, diarrhoea, or extreme fatigue, or other symptoms recognized in local and international guidelines as typical of mild COVID-19.
6. SARS-CoV-2 infection confirmed through a positive LumiraDx™ rapid antigen test on the day of screening or a positive RT-PCR within two days prior to screening.
7. Participant is at high risk for progression to severe COVID-19, this defined as either:
 - a. Age ≥ 50 with at least one of the following background or medical conditions: diabetes mellitus, obesity ($BMI \geq 30 \text{ kg/m}^2$), hypertension, HIV, active or previous TB.
 - b. Age ≥ 65
8. Participant agrees to comply with study procedures, including the completion of a daily diary for 10 days from the time of enrolment, and to be available for study contacts and visits.

5.2 Exclusion criteria:

1. Pregnant or breastfeeding women, or women planning/desiring to become pregnant during the 28 days following enrolment into the study.
2. Duration of self-reported symptoms of COVID-19 for more than five days prior to screening.
3. Signs of respiratory distress or severe disease prior to enrolment, including:

- a. respiratory rate >24 breaths/min
- b. SpO2 <95% in room air
- c. heart rate ≥120 bpm
- d. abnormal mental status
- e. inability to walk due to COVID-19 symptoms
- f. inability to talk in full sentences due to COVID-19 symptoms
- g. a requirement for hospitalisation.

4. Inability/unlikely to be in the study area for the duration of the 28-day follow-up period.
5. Inability to tolerate oral medications.
6. Any surgical or medical condition which might significantly alter the absorption, distribution, metabolism, or excretion of drugs, or which may jeopardize the safety of the patient or the objectives of the study. The Investigator should make this determination in consideration of the volunteer's medical history.
7. The volunteer is assessed to be clinically unstable in the Investigator's opinion.
8. Participation in another investigational study involving an investigational product within 30 days, or 5 half-lives, whichever is longer, prior to screening.
9. Personnel (e.g., investigator, sub-investigator, research assistant, pharmacist, study coordinator or anyone mentioned in the delegation log) directly involved in the conduct of the study.
10. Any physical, mental, or social condition, drug/alcohol use, history of illness or laboratory abnormality that, in the Investigator's judgment, might jeopardise the safety of the patient in the context of this study, or might interfere with study procedures or the ability of the subject to adhere to and complete the study. The Investigator should make this determination in consideration of the volunteer's medical history.

5.3 Justification of the Inclusion and Exclusion Criteria

The eligibility criteria have been selected to minimise risk to the well-being of participants in this study. The criteria are also set to ensure that the study population closely approximates the real-life target population of molnupiravir (i.e., intended recipients of a therapeutic agent known to reduce the risks of severe progression of mild COVID-19 in the South Africa setting).

5.4 Participant Identification

All volunteers who are screened for eligibility to participate in the study will be allocated a unique sequential screening number which will be used as the primary identifier for the duration of the study for enrolled participants.

5.5 Co-enrolment Guidelines

Participants may be co-enrolled in other research studies if these are observational in nature or include behavioural interventions only. Any other exception requires approval by the Principal Investigator in consultation with the Medical Monitor.

6. STUDY TREATMENTS

6.1 Molnupiravir

Molnupiravir is a broad-spectrum antiviral that is an orally bioavailable prodrug of the nucleoside analogue NHC. NHC distributes into cells where it is phosphorylated to form the pharmacologically active NHC-TP. NHC-TP acts by a mechanism known as viral error catastrophe. NHC-TP incorporation into viral RNA by the viral RNA polymerase, results in an accumulation of errors in the viral genome leading to inhibition of replication.

6.1.1 Packaging, labelling, storage, and accountability

Adequate quantities of molnupiravir will be supplied in pre-packaged quantities (each sufficient for a five-day treatment course for one patient) to the study site once approvals from the South African Health Products Regulatory Authority (SAHPRA) and relevant IRB/EC(s) have been obtained. The drug will be packed, labelled, and shipped together with the respective Certificates of Analysis containing the batch numbers.

The label content will be in accordance with South African legal requirements.

The Principal Investigator is responsible for ensuring that the study drug is stored in a secure location with restricted access to unauthorised personnel. Molnupiravir should be stored at room temperature. Storage conditions must be adequately monitored, and appropriate temperature logs maintained throughout the study.

Upon receipt of the molnupiravir shipment, the study pharmacist (or designee) must immediately inspect the shipment for damage, acknowledge receipt and confirm the shipment condition and content. Any damage or discrepancies from the packing list must be documented and promptly discussed with the supplier and study monitor to determine the appropriate action.

The study pharmacist (or designee) is responsible for maintaining accurate study drug accountability records. Instructions and the necessary forms for completion will be detailed in the Pharmacy Manual. Study drug accountability records will be reviewed by the study monitor during interim site visits and upon completion of the study. On study completion, copies of all study drug management records will be provided to the Sponsor. The originals must be maintained at the study site with the rest of the study records.

6.1.2 Cohorts

Eligible participants will be randomised in a 1:1 manner to receive either molnupiravir 800 mg orally approximately 12-hourly for five days or a placebo for the equivalent amount of time.

6.1.3 Blinding

The study will be double-blind. Neither the participants nor the principal investigator (or designee) who will be assessing AEs, will know the treatment group. A participant's treatment assignment may only be unblinded when knowledge of the treatment is essential for the safety of the participant and following consultation with the medical monitor. The process for unblinding will be documented in a Study Unblinding Plan.

6.1.4 Dispensing

Study drug (and home monitoring kits) will either be dispensed to participants at the site or delivered to participants at their homes.

6.1.5 IMP administration

Molnupiravir capsules can be taken with or without food. Each dose should be swallowed whole with fluid (e.g., a glass of water). The capsules should not be opened, crushed or chewed.

Participants will be provided with dosing instructions at the time of enrolment and when study drug is dispensed. They will self-administer the study treatment approximately 12-hourly for five days (10 consecutive doses).

6.1.6 Treatment compliance

All participants will be asked to complete a daily survey to gather information regarding treatment compliance.

If the participant notices that they have missed a dose of molnupiravir within 10 hours of the time that it was scheduled, they should take the missed dose as soon as possible and resume the normal dosing schedule thereafter. If a participant misses a dose by more than 10 hours, they should not take the missed dose and instead take the next dose at the regularly scheduled time. The participant should not double the dose to make up for a missed dose.

6.1.7 Overdose

There is no human experience of overdosage with molnupiravir. Treatment of overdose should consist of general supportive measures as required, including the monitoring of the clinical status of the patient. Haemodialysis is not expected to result in effective elimination of NHC.

6.1.8 Returns and destruction

After study completion and on the receipt of written authorisation from the Funder, any remaining study drug supplies will either be returned to [name] company or will be destroyed at a defined location. Details of the final disposition of unused study drug, including a copy of the destruction certificate as relevant, will be documented in the Trial Master File.

6.2 Concomitant Therapy and Lifestyle and Dietary Restrictions

6.2.1 Concomitant treatments

Participants will be asked about concomitant medications at the screening evaluation visits. At each contact, the Investigator should question the participant about any medication taken (including over-the-counter or prescription medicines, vitamins, and/or herbal supplements). All concomitant medications, vaccines, dietary supplements and herbal or traditional preparations taken from 28 days prior to study vaccine administration until the final safety follow-up visit will be detailed in the eCRF.

No concomitant treatments are prohibited during the study.

6.2.2 Lifestyle restrictions

The following lifestyle restrictions apply for participants enrolled in the study:

- Female participants should avoid becoming pregnant for the duration of the study.

- Women of reproductive potential must continue to use a highly effective method of contraception (as detailed in Section 5.1) during the study.
- Male participants will be advised to wear a condom when engaging in any activity that allows for passage of ejaculate to another while taking the investigational product. Male participants should also be advised of the benefit for a female partner to use a highly effective method of contraception as condom may break or leak.
- Female participants should not breast-feed during the study.

6.3 After Study Treatment

No additional treatment (prophylactic or therapeutic) will be provided at the end of the study.

7. STUDY VISITS

The planned visit schedule, associated visit window periods, and assessments and procedures to be conducted at each visit are detailed in the Section 1 (Schedule of Events [SOE]). Details regarding each assessment and procedure are described in Section 8.

Contact between study participants and study personnel will be limited as far as is possible. Study personnel will be instructed to wear appropriate PPE during all interactions, and participant and study personnel will be instructed to adhere to national and regional guidance for COVID-19-related safety measures.

For this study, data collection will be self-conducted where possible to minimize the impact of non-ill participants within the healthcare system and the risks of SARS-CoV-2 transmission. If the participant is assessed as eligible during the screening visit, contact between study participants and study personnel will occur via telephone, text/direct messaging, or tele-medicine, as far as is possible.

Participants will be instructed to seek clinical care should they manifest any signs or symptoms of a lower respiratory tract infection (LRTI) requiring medical intervention and notify their physician about trial participation. Any participant whose clinical condition deteriorates during the study, will be hospitalised if required in accordance with the national guidelines for clinical management of patients with COVID-19¹⁸.

8. STUDY ASSESSMENTS AND PROCEDURES

No study-specific assessments will be performed, or information gathered, until the potential participant has given written, informed consent (Section 12.2) for screening procedures and (if found to be eligible) for procedures and assessments to be conducted during the study period.

The timing of all assessments and procedures is detailed in the SOE (Section 1).

8.1 Screening and Baseline Assessments

Screening evaluations must be completed, and the results reviewed by the Investigator to confirm eligibility of participants. A maximum of 1 calendar day is permitted between screening evaluations and the initiation of study drug, although in most cases, it is anticipated that these will be performed on the same day.

8.1.1 Demographics and social habits data

Demographic and baseline characteristic data to be collected for all participants includes age, sex, reproductive potential, self-reported race and predominant ethnicity.

8.1.2 Relevant medical and surgical history/current medical conditions including treatment

Information related to past and current relevant medical conditions and surgical procedures will be collected, including previous COVID-19, pregnancy and/or lactation status. In addition to the age of the participant, the presence of the following risk factors for disease progression will be noted:

- Obesity (BMI $\geq 30.0 \text{ kg/m}^2$)
- Diabetes mellitus
- Hypertension
- HIV
- Active or previous TB.

COVID-19 vaccination history, and current and previous medication usage, including contraception as relevant, will be ascertained and interpreted as relevant to the study-specific eligibility criteria.

Collection of information regarding illicit drug and alcohol consumption will be collected to enable assessment of eligibility.

8.1.3 Screening-specific special investigations

8.1.3.1 Rapid antigen test

Anterior nasal or nasopharyngeal swabs will be collected from all potentially eligible volunteers at screening on Day 0 for qualitative detection of SARS-CoV-2 nucleocapsid protein antigen. Swabs from other anatomical sites may be used based on emerging recommendations detailed in the LumiraDx™ SARS-CoV-2 Antigen [Ag] test specifications.

Details regarding sample collection, handling and processing, the assays and interpretation of the results, will be documented in the Laboratory Manual.

Patients that have tested positive by same-day LumiraDx™ SARS-CoV-2 Ag from another vendor or have a laboratory confirmation of an RT-PCR positive for SARS-CoV-2 within 2 days prior to screening, will not require an additional rapid antigen test at screening.

8.1.3.2 Pregnancy test

A point-of-care high sensitivity β -HCG urine pregnancy test will be conducted for all women of reproductive potential at screening to assess eligibility, at the EOS visit, and during unscheduled visits if deemed necessary by the Investigator.

Women are considered post-menopausal and/or not of reproductive potential if they have had at least 12 months of natural (spontaneous) amenorrhea with an appropriate clinical profile (e.g., age appropriate, history of vasomotor symptoms) or six months of spontaneous amenorrhea with local laboratory serum follicle stimulating hormone (FSH) levels (performed as standard of care i.e., not a study-specific procedure) commensurate for post menopause; or have had surgical bilateral oophorectomy or bilateral salpingectomy (with or without hysterectomy) at least six months prior to screening.

8.1.3.3 Optional HIV Test

An optional point-of-care HIV antibody test will be offered to all participants at screening. All participants who test positive will be referred to their local clinics for care.

***Participants who test negative for COVID antigen, or are pregnant, will be screened failed, and no further screening study procedures will be done (except for the collection of patient demographics).**

8.2 Safety Assessments

8.2.1 Physical examination

Abbreviated, symptom-directed physical examinations will be performed at screening, at the EOS visit, and during unscheduled visits if deemed necessary by the Investigator. At a minimum these examinations will include:

- general appearance
- skin
- heart / circulation
- chest and lungs.

Significant findings present at screening will be recorded in the relevant medical history/current medical conditions section of the participant's eCRF. Significant findings, or worsening of pre-existing findings, detected after dosing will be recorded as adverse events in the participant's eCRF.

8.2.2 Height and weight

Height in centimetres (cm) and body weight (to the nearest 0.1 kg in light indoor clothing, but without shoes) will be measured.

Body Mass Index (BMI) will be calculated using the formula: BMI = weight (kg) / height (m)².

8.2.3 Vital signs

Vital signs include body temperature, pulse rate, blood pressure assessments and SpO₂. Blood pressure, pulse rate and SpO₂ will be measured after the participant has been at rest for at least 5 minutes in accordance with the timepoints detailed in the SOE (Section **Error! Reference source not found.**). An appropriately sized cuff will be used to ensure accurate blood pressure determination.

8.2.4 Laboratory evaluations

8.2.4.1 Safety laboratory assessments

No scheduled safety laboratory assessments are planned. *Ad hoc* laboratory evaluations may be conducted for participants requiring specific safety monitoring of emergent adverse events.

8.3 Efficacy Assessments

8.3.1 Patient Reported Outcomes

Participants will be asked to complete the following surveys during the study:

- The FLU-PRO[®] Plus questionnaire¹⁹⁻²¹ to assess the symptomatic extent of their illness (Appendix 2)
- The daily survey (Appendix 3) that includes:

- The FLU-PRO[®] Plus Global Additional Daily Diary Items (related to general well-being, overall severity of symptoms, and ability to perform usual daily activities)
- General daily diary items (related to study drug administration, recording of vital signs and SpO₂ measurements, review of concomitant medications, and information related to possible adverse events).

These surveys will be completed electronically or using a participant diary. Participants will be contacted via telephone call or text/direct messaging or web-based conference on day 3/6/10 by a staff member to confirm any AE occurrence, general well-being and update the WHO clinical progression scale. The participants will fill in the surveys daily themselves for 10 days, these will be collected at EOS or if electronically captured, before then.

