1. SCHEDULE OF EVENTS

Procedure / assessment	Screening/ Enrolment	Treatment and Follow-Up (including self-quarantine as required in accordance with local guidelines)							EOS Day 29 (±3) ^b
	Day 0 ^a	Day 1-2	Day 3	Day 4-5	Day 6	Day 7-9	Day 10		
Informed consent	X								
Demography	X								
Duration of COVID-19 symptoms	X								
Pregnancy and lactation status ^c	X								
Urine pregnancy test ^d	X								
LumiraDx™ SARS-CoV-2 Ag testing ^e	X								
Point of Care HIV test ^f									
Past and current medical conditions (including COVID-19 vaccination status)	X								
Concomitant medications, including contraception	X		X		X			X	X
Physical examination, including weight and height ^g	X								X
Vital signs (temp., pulse, BP, RR, SpO2) ^h	X								X
Eligibility criteria	X								
WHO Clinical Progression Scale ⁱ	X		X		X			X	X
Study treatment ^j		X	X	X					
Patient reported vital signs (temp., pulse and SpO2) ^k		X	X	X	X	X	X		
Completion of daily survey and FLU-PRO® Plus questionnaire ^l		X	X	X	X	X	X		X
Adverse event review ^m			X		X			X	X
Return of unused IMP and empty containers									X ^m
Contact with study staff ⁿ	X		X		X			X	

EOS: end of study; temp.: body temperature; BP: blood pressure; RR: respiratory rate; SpO2: oxygen saturation; WHO: World Health Organization.

Note: Participants who stop study product should continue study participation off study product with continued evaluations as per the schedule of activities. The reason for study product discontinuation should be recorded.

^a A window period of -1 day may apply in cases where COVID-19 symptoms have not already been present for 5 days at the time of screening. Screening/enrolment (Day 0) and initiation of study treatment and follow-up (Day 1) are anticipated to occur on the same day for most participants.

^b For participants who are hospitalized at the time of the scheduled Day 29 visit, the EOS visit will be approximately 3 days after discharge.

^c Female participants only.

^d Urine pregnancy test for women of reproductive potential only.

- ^e Participants with same-day LumiraDx SARS-CoV-2 Ag from another vendor or a laboratory confirmation of an RT-PCR positive for SARS-CoV-2 within 2 days prior to screening will not require an additional rapid antigen test.
- ^f Optional HIV point of care testing will be offered to participants at screening. Newly diagnosed patients will be referred appropriately for care.

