- ^g An abbreviated, symptom-directed physical examination including at least a general examination and chest auscultation will be performed. Height will be measured at screening only.
- ^h Body temperature will be measured. Pulse, RR and SpO₂ will be measured after at least 5 minutes resting.
- ⁱ To be performed via telephone call or text/direct messaging or web-based conference, or in person as necessary. For the Day 3, 6 and 10 contact sessions, a window period of ± 1 days is permitted. This window period will also apply to the assessment of the WHO Clinical Progression Scale score by the study team personnel, and the review of adverse event and concomitant medication data to be performed during these contact sessions.
- ^j Molnupiravir 800 mg will be taken approximately 12-hourly, with a glass of water, with or without food, for five days (10 doses).
- ^k The Day 1 assessments will be performed by enrolled participants under observation of the study personnel. Assessments will be recorded utilizing a mobile phone/tablet application, or other device, or diary, or during a telephonic or in person interaction with the site personnel. Assessments may be performed by study personnel if an in-person visit is conducted after completion of the quarantine period.
- ^l The FLU-PRO[®] Plus questionnaire and daily survey will be recorded daily for 10 days by participant utilizing a mobile phone/tablet application or diary. The daily survey will consist of the FLU-PRO[®] Plus Global Additional Daily Diary Items (related to general well-being, overall severity of symptoms, and ability to perform usual daily activities) as well as other general daily diary questions related to study drug administration, recording of vital signs and SpO₂ measurements, review of concomitant medications, and information related to possible adverse events.
- ^m Serious adverse events, adverse events resulting in treatment discontinuation, and all other AEs, including those judged by the site Investigator to be related to the administered treatment regimens.
- ⁿ Or anytime from Day 6 if an earlier contact visit takes place.

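### Paper-diary SpO2 readings from Days 2-10 need not reach staff until the end-of-study visit, 16 to 30 days after they are taken

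*Protocol*

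**What the plan says.** Section 8.3.1 makes home vital signs and SpO2 part of the daily survey and lets participants complete the surveys electronically or in a diary. It then fixes when they reach staff: "these will be collected at EOS or if electronically captured, before then". EOS is Day 29 ±3. For a participant in hospital at that time, Schedule of Events footnote b says "the EOS visit will be approximately 3 days after discharge".

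The Day 3, 6 and 10 contacts are defined in two places. Section 8.3.1 says staff make them "to confirm any AE occurrence, general well-being and update the WHO clinical progression scale". Footnote i gives them a window of ±1 day and adds "the review of adverse event and concomitant medication data to be performed during these contact sessions".

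Three other provisions bear on the point:

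- Footnote k has staff observe the Day 1 measurements. It then lists ways to record the readings: an app, another device, "or diary, or during a telephonic or in person interaction with the site personnel".
- Footnote n foresees a possible earlier visit: "Or anytime from Day 6 if an earlier contact visit takes place".
- Section 7 instructs participants to "seek clinical care should they manifest any signs or symptoms of a lower respiratory tract infection (LRTI) requiring medical intervention".

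Exclusion criterion 3b in section 5.2 bars anyone with "SpO2 <95% in room air", listing it among the signs of severe disease.

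**The concern.** These are adults aged 50 or over, enrolled because they are at high risk of progression and measuring themselves at home in the days when they may deteriorate. Between Day 1 and EOS the Schedule of Events has no staff-measured vital signs, and section 8.2.4.1 plans no scheduled safety laboratory tests. The home readings are then the only scheduled objective physiological data.

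An SpO2 that would have kept the person out of the trial at screening can be written on paper at home, with no required step that shows it to staff until about three weeks after dosing ends. Section 9.2.2 asks for a judgement on whether a vital-sign abnormality is clinically significant. For these readings that judgement comes too late to help the participant.

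This is a patient-safety point. No loss of data and no bias between arms is claimed. Day 1 readings are observed and electronic entries arrive earlier, so the point is confined to Days 2-10 in paper-diary users.

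**Working it through.** The protocol states no delay figure, so there is none to reproduce.

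**Is there a required route to staff before EOS?**

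| Provision | Does it require staff to obtain a paper reading before EOS? |
|---|---|
| 8.3.1, survey collection | No. Collection is at EOS unless electronic |
| 8.3.1 and footnote i, contact tasks | No. Adverse events, well-being, WHO scale, concomitant medication |
| Footnote k, recording routes | No. Telephone recording is one permitted option |
| Footnote n, visit from Day 6 | No. Only if such a visit takes place |
| Section 7, seek-care instruction | No. It depends on the participant, and gives no SpO2 value |
| Appendix 3, item 4 (changes or new complaints) | No. For a paper user the answer is in the same uncollected diary |
| Appendix 4, WHO scale | No. Ambulatory states are scored without SpO2 |

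**Inputs.** Unobserved home readings fall on days d = 2 to 10, nine per participant (Schedule of Events, footnote k). EOS is Day 26 to Day 32 (29 ±3). Contacts are on Days 3, 6 and 10, each ±1 day. The last dosing day is Day 5.

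**Current delay = EOS day − d**

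- Shortest: 26 − 10 = 16 days.
- Longest: 32 − 2 = 30 days.
- EOS on Day 29: from 29 − 10 = 19 to 29 − 2 = 27 days. The mean reading day is 6, so the mean delay is 29 − 6 = 23 days.
- EOS after the last dosing day: 26 − 5 = 21 to 32 − 5 = 27 days.

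**Delay if readings are obtained at each contact (nominal days) = next contact day − d**

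| Reading day | 2 | 3 | 4 | 5 | 6 | 7 | 8 | 9 | 10 |
|---|---|---|---|---|---|---|---|---|---|
| Next contact | 3 | 3 | 6 | 6 | 6 | 10 | 10 | 10 | 10 |
| Delay (days) | 1 | 0 | 2 | 1 | 0 | 3 | 2 | 1 | 0 |

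The sum is 10, the mean 10/9 = 1.1 and the maximum 3. The mean gain with EOS on Day 29 is 23 − 1.1 = 21.9 days.

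**At the window limits** (contacts on Days 2-4, 5-7 and 9-11)

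- The worst case is a Day 6 reading with contacts on Days 5 and 11: 11 − 6 = 5 days.
- If the Day 5 reading is taken after a Day 5 call: 11 − 5 = 6 days.
- If the last contact is held on Day 9, the Day 10 reading falls outside all contacts and still waits 26 − 10 = 16 to 32 − 10 = 22 days. A rule to obtain it by Day 11 cuts this to 1 day.

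**The case against.** The strongest reply is that 8.3.1 says when forms are handed in and does not describe safety surveillance. Section 9.1.4 gives medical review to a Medical Monitoring Plan to be finalised before the first enrolment, and section 9.1.1 makes the Principal Investigator responsible for close monitoring. Footnote k already allows readings to be taken by telephone. Staff speak to or message every participant three times by about Day 10, ask about adverse events and well-being, and score the WHO scale. The 16 to 30 days is how long a paper form waits. It is not how long a deteriorating patient goes unobserved. Harm needs a chain: a paper user with a truly low value that is not recognised, not mentioned at any remaining contact, not accompanied by visible decline, and not acted on.

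Much of this is fair, and it limits the point. The delay figures describe when staff must have the reading, the affected group may be small, and the monitoring plan, which is not available here, may add a step. It does not close the gap. None of these provisions requires the readings to be obtained, and a monitoring plan cannot review paper data that have not been collected. The protocol sets the collection time itself.

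A second objection is that passing numbers to staff without an SpO2 threshold leaves the participant's failure to recognise a low value untouched. That is true of same-day recognition. It does not make the change unsound, because staff who have the value can make the section 9.2.2 judgement while the participant may still benefit.

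**Conclusion.** The concern holds. For paper-diary users, the protocol requires no step that brings a Day 2-10 home reading to staff until EOS, 16 to 30 days later (19 to 27 days, mean 23, with EOS on Day 29).

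This assumes that the participant uses paper, attends EOS within its window, and does not recognise, mention or act on the low value. Early withdrawal can bring collection forward, because section 4.4 asks for the EOS assessments at that point. Hospitalisation on Day 29 can push it past Day 32, but that participant is already under care.

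The paper share and the frequency of unrecognised low readings are not given, so no count of affected participants is possible. The point is a worthwhile safety improvement; it does not touch the hospitalisation or death endpoint or its analysis. Confidence is medium, because an operational document may already ask for the readings.

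**What to change.** Amend section 8.3.1 and the Schedule of Events to say:

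- At each Day 3, 6 and 10 contact, staff obtain the pulse, temperature and SpO2 values recorded since the previous contact. Paper-diary users read them out; electronic entries are reviewed on the system. Staff enter the values in the eCRF for the section 9.2.2 judgement.
- Any reading taken after the last contact, for example when the Day 10 contact is held on Day 9, is obtained by call or message by Day 11.

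No new visit, endpoint, analysis or clinical action rule is needed.

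The cost is a few extra minutes on calls already planned, plus one message when the last contact precedes the Day 10 reading. Home oximeter error will bring some false low values to staff and prompt some unneeded checks, equally in both blinded arms. The change shortens the delay but does not remove it: up to 3 days on nominal contact days, and 5 or 6 at the window limits.
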